C.1.b. Impact of a Provider Communication Strategy on Parental Vaccine Hesitancy Towards Childhood Vaccines ([name], Co-I): [name] et al. conducted a cluster RCT of 56 pediatric and family medicine clinics in the greater Seattle metropolitan area to test the effect of a provider communication strategy on parental vaccine hesitancy.²⁸ There were 26 clinics in the control arm in which parents of newborns received usual care and 30 clinics in the intervention arm in which providers received training on a communication strategy called: "Ask, Acknowledge, and Advise." The centerpiece of this strategy was an algorithm in which providers were first encouraged to begin the vaccine recommendation by asking parents what questions they had about the immunization schedule, then acknowledging parental vaccine concerns, and finally, advising parents in a manner specific to their concerns. The intervention training included a well-attended (68% of providers) didactic session at baseline that incorporated videos of providers modeling the communication strategy. Providers in intervention clinics also received paper materials detailing the framework as well as monthly e-mail newsletters and a link to the study website that included a webinar version of the training.

Our primary outcome was the change in the proportion of parents who were VHPs (as measured by the PACV) at recruitment after the birth of their child and follow-up when the child was 6 months old. We found that among all enrolled parents, 11.3% were VHPs. The proportion of VHPs at baseline and follow-up changed

Table 1. PACV-SF: Positive if ≥ 2 hesitant responses

No.	Item	Hesitant Response
1	Have you ever delayed having your child get a shot for reasons other than illness or allergy?*	Yes
2	How concerned are you that a shot might not prevent the disease?	Very concerned, somewhat concerned, or not sure
3	Overall, how hesitant about childhood shots would you consider yourself to be?	Very hesitant, somewhat hesitant, or not sure
4	I trust the information I receive about shots.	Strongly disagree, disagree, or not sure

*Only delay of the birth dose of the hepatitis B vaccine would be relevant for parents of children ≤ 2 months old, as was used and evaluated in a prior study¹⁸

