C.6.e. Covariate-constrained Randomization: Practices will be the unit of randomization. A key issue in cluster-randomized trials is the possibility of covariate imbalance in practices assigned to different treatment arms.¹⁰⁴⁻¹⁰⁸ Thus, practices will be randomly assigned to assure balanced comparison groups using optimized probability sampling to the intervention or control arm in the following manner. From the pool of practices that agree to participate in the study, pre-study information will be collected on several characteristics that may influence study outcomes: percent of VHPs, percent of Vaccines-for-Children [VFC]-eligible patients, number of pediatric providers, and practice immunization rates of children 19-35 months old. These pre-study variables will then be used to develop and evaluate a balance criterion, defined as the sum of the squared differences between standardized practice means on these variables.¹⁰⁵ All possible combinations of eligible practices in 2 arms (intervention and control) will be generated using a SAS macro program.¹⁰⁷ The distribution of the balance criterion for the 2 study arms will be used to define an acceptable set of study arms that are reasonably balanced in terms of the selected variables (minimum 10% of balance criterion).¹⁰⁵ From this set, one set will be chosen at random and used to randomly assign each practice to intervention or control arms. This process will be undertaken in both Colorado and Washington as separate randomization procedures. We have successfully used covariate-constrained randomization in C.1.d. and other studies.^{109,110}

We will perform the following procedures to obtain pre-study information on these covariates:

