C.6.e.4. Assessment of the proportion of children who are up-to-date (UTD) on immunizations at each practice: We will conduct a retrospective analysis of UTD status for all recommended childhood vaccines among children 19-35 months old at each practice using vaccine administration data for each practice obtained from the two state's immunization registries (WAIIS and CIIS). The WAIIS and CIIS operate in accordance with nationally recommended standards for immunization registries, and all PSPRN and COCONet practices participate in CIIS or WAIIS. Both CIIS and WAIIS use birth certificate data to identify children and cover ≥95% of children <6 years old in their respective states.¹¹¹ Both CIIS and WAIIS¹¹² combine the immunization information from multiple sources into a consolidated, complete, and valid record of immunizations. Data quality assessments are done frequently. Offices are required to have <5% error rate in the registry, making these registries a highly accurate data source for assessing vaccine utilization.

C.6.f. Intervention: Intervention specifics will ultimately be determined through the iterative process detailed in Aim 1 (see *C.5.c.-d.*). Therefore, what follows is preliminary and will be modified. At baseline, providers at intervention practices will be electronically sent a link to the online video module to view at their convenience. Modules will be approximately 30 minutes and will be encoded with a viewing tracker that will enable study staff to monitor its completion. Providers who have not viewed the module within 2 weeks will be sent up to 3 reminders with additional links to the video module. The window for viewing the video module will be 30 days, and viewing the video will be required for provider to receive MOC Part 4 credit. Based on our previous study utilizing a baseline video module (see *C.1.d.*), we expect a $\geq 70\%$ completion rate.

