C.6.h. Blinding: Given our intervention, it is not possible to blind providers or investigators to study-arm allocation. However, our analysts will be blinded to study-arm allocation. We will also minimize selection bias by including all parents whose newborns receive health supervision at participating practices in the study and analysis. We will minimize participant bias by blinding providers to PACV-SF scores of parents and parent ascertainment bias by masking the PACV-SF during enrollment by embedding it in a larger survey.

C.6.i. Primary Study Outcome: Our primary outcome will be the immunization status of children of VHPs at 19 months, 0 days of age expressed as the mean percentage of days under-immunized from birth to 19 months for 22 doses of 8 vaccines recommended during this interval (3 Hepatitis B, 3 Rotavirus, 4 Diphtheria, tetanus, and acellular pertussis [DTaP], 3 *Haemophilus influenzae*, type b [Hib], 4 Pneumococcal conjugate, 3 Inactivated poliovirus [IPV], 1 Measles, mumps, rubella [MMR], and 1 Varicella). To calculate the mean percentage of days under-immunized, we will sum the days late for each dose and divide this by the maximum number of days a child could be late if they had received none of the total 22 doses for the 8 vaccines by 19 months. We have chosen to use the mean percentage of days under-immunized because it is a sensitive measure of under-immunization by accounting for missed vaccines doses and delay in receipt of vaccines.¹¹⁷ We have successfully used this measure in previous studies (see C.1.a. and C.1.c.). We will obtain immunization data from WAIIS and CIIS as described in C.6.e.4. As an exploratory secondary outcome, we will also measure the immunization status of children of non-VHPs (expressed as the mean percentage of days under-immunized) since the PIVOT with MI intervention involves use of the presumptive format with all patients and therefore has the potential to also impact the vaccine behavior of non-VHPs.

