age for 6 vaccines combined (Hepatitis B, DTaP, Hib, IPV, MMR, and Varicella).¹⁸ This corresponds to an average of 37 days late per vaccine dose. To be able to detect with adequate power ($\geq 90\%$) a decrease in under-immunization of 10 days—a decrease that has the potential to be clinically meaningful since 27 days would not be considered late for most vaccines because of the 30 day window in which most vaccine doses are recommended¹²¹—we need to enroll 600 VHP/newborn pairs total, with 300 per arm and 25 at each of the 24 study practices (assuming an α of 0.05, a SD of 20, and an intraclass correlation coefficient for within-clinic correlation of 0.02²⁸). Assuming a 10% prevalence of VHPs (see C.1.b),²⁸ we will need to approach 6,000 parents to reach our sample size goal. This is feasible to achieve in our designated 18 month recruitment period given our design to integrate PACV-SF screening of parents of newborns into standard practice workflow and our estimate (determined by spot chart reviews at PSPRN and COCONet practices) that there are ≥ 10 newborns per clinic per week in PSPRN and COCONet practices. If we vary our assumptions regarding VHP prevalence (7.5%) or SD (25), we would need to approach 8,000 and 12,000 parents, respectively, for adequate ($\geq 90\%$) power to detect the same effect size, both of which remain feasible within the 18 month enrollment period assuming ≥ 10 newborns per clinic per week. If we have unbalanced enrollment across study arms (i.e. not 1:1 enrollment in intervention and control arms), we will continue enrollment beyond 600 VHP/newborn pairs total in order to reach at least 300 VHP/newborn pairs per arm given the impact of an imbalance on our power.

For our fidelity outcome (Aim 2a), power can be considered in terms of the number of videotaped interactions needed to develop this coding scheme. Based on our prior studies (see C.1.c.), 3 videotaped visits per provider should be adequate to achieve sufficient behavioral variation across providers. We will therefore videotape up to 360 encounters (up to 180 in each state), which averages to 3 videotaped encounters per practice provider.

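### The pre-study registry data are scored only as an up-to-date rate, no practice-level baseline of the primary outcome is pre-specified as a model covariate, and the ICC of 0.02, cited to a trial of parental hesitancy, is not varied

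*Combined protocol and SAP*

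**What the plan says.** **Baseline measure.** C.6.e.4 takes vaccine administration data from the Washington and Colorado registries: "We will conduct a retrospective analysis of UTD status for all recommended childhood vaccines among children 19-35 months old at each practice". C.6.e lists the result, "practice immunization rates of children 19-35 months old", as one of four variables in the balance criterion. The others are percent of vaccine-hesitant parents (VHPs), percent of patients eligible for Vaccines for Children, and number of pediatric providers.

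**Primary outcome.** C.6.i uses the same registries, but computes the percentage of days under-immunized from birth to 19 months 0 days for 22 doses of 8 vaccines, in children of VHPs only. It gives the reason for this metric: "because it is a sensitive measure of under-immunization by accounting for missed vaccines doses and delay in receipt of vaccines".

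**Adjustment.** Model (1) in C.6.j admits covariates at patient, provider or practice level. The only rule for choosing them is that confounders found unbalanced at baseline are included. Neither the up-to-date rate nor any other practice baseline of the outcome is named.

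**Power.** C.6.k plans 600 pairs (300 per arm, 25 at each of 24 practices), "assuming an α of 0.05, a SD of 20" and an ICC of 0.02, for power of at least 90%. The ICC carries the same reference number as the trial described in C.1.b, of which the plan says: "Our primary outcome was the change in the proportion of parents who were VHPs (as measured by the PACV". The alternative scenarios in C.6.k change VHP prevalence (7.5%) and SD (25). None changes the ICC.

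**The concern.** An up-to-date rate is a dichotomy. C.6.e.4 fixes no single assessment age between 19 and 35 months, so on one reading a child who was months late but later caught up counts the same as a child vaccinated on time. That is the delay information for which C.6.i chose its metric. Every child aged 19 months or more has a complete birth-to-19-month history, so if the extract carries dose dates the C.6.i formula can be applied to it directly.

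With 24 practices, variation between practices is a sizeable part of the error in the arm difference. A baseline in the outcome's own metric is a natural candidate to explain some of it, but only if it is in the model. A rule triggered by observed imbalance does not ensure that.

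The same variation drives the design effect. The ICC is cited to a trial with an attitudinal, binary primary outcome, while this outcome is continuous and registry-based. How far the power claim depends on that value is not shown.

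**Working it through.** **Inputs from C.6.k:** 300 per arm, m = 25 per practice, 12 practices per arm, SD 20, alpha 0.05 (taken as two-sided), ICC 0.02. The target is "a decrease in under-immunization of 10 days". The plan equates a mean of 26.2% with 37 days late per dose, so the target is 26.2 × 10/37 = 7.08 percentage points. SD 20 is read as percentage points.

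**Step 1. Reproduce the plan.**
Design effect = 1 + (m − 1) × ICC = 1 + 24 × 0.02 = 1.48.
SE = 20 × √(2 × 1.48/300) = 1.987.
7.08/1.987 = 3.564.
Power = 94.6% (normal) or 92.6% (noncentral t, 22 df = 24 practices − 2). The stated 90% or more is met.

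**Step 2. Vary the ICC, all else as planned.** The range is an assumption, because the documents give no ICC for this outcome.

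| ICC | Design effect | SE | Power, normal | Power, t 22 df |
|---|---|---|---|---|
| 0.01 | 1.24 | 1.818 | 97.3% | 96.1% |
| 0.02 | 1.48 | 1.987 | 94.6% | 92.6% |
| 0.03 | 1.72 | 2.142 | 91.1% | 88.5% |
| 0.05 | 2.20 | 2.422 | 83.2% | 79.8% |

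Power falls below 90% once the ICC exceeds about 0.033 (normal) or 0.026 (t).

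**Step 3. How much of the variance lies between practices?**
Share = m × ICC / design effect.
ICC 0.02: 0.50/1.48 = 34%. ICC 0.05: 1.25/2.20 = 57%.

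**Step 4. What could a practice-level covariate recover?** Let r be the correlation between the baseline and the practice's later level among children of VHPs. The design effect becomes (1 − ICC) + m × ICC × (1 − r²). The documents give no r, so 0.5 and 0.7 are assumed, as examples of a weaker and a stronger baseline.

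| ICC | r | Design effect | Variance removed | Power, normal | Power, t 21 df |
|---|---|---|---|---|---|
| 0.02 | 0.5 | 0.98 + 0.50 × 0.75 = 1.355 | 8% | 96.1% | 94.4% |
| 0.02 | 0.7 | 0.98 + 0.50 × 0.51 = 1.235 | 17% | 97.4% | 96.1% |
| 0.05 | 0.5 | 0.95 + 1.25 × 0.75 = 1.8875 | 14% | 88.4% | 85.3% |
| 0.05 | 0.7 | 0.95 + 1.25 × 0.51 = 1.5875 | 28% | 93.1% | 90.7% |

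The t column uses 21 df because the covariate costs one between-practice degree of freedom. Moving from r = 0.5 to r = 0.7 adds under 2 points of power at ICC 0.02 and about 5 points at ICC 0.05.

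**Step 5. Whose ICC can the extract supply?** C.6.e.1 screens parents of newborns only, starting 2 months before the intervention. Children already 19-35 months old therefore have no recorded hesitancy status. The extract can give an ICC of days under-immunized among all children, but not among children of VHPs, the primary analysis population.

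**The case against.** The up-to-date rate is a legitimate balance variable, and it is used beside percent VHP and percent Vaccines-for-Children eligible. Choosing it is not an error. At the plan's own ICC the power claim is met, and the gain from a better baseline is small. The gain also rests on assumed correlations: if the rescored mean predicts no better than the up-to-date rate, nothing is gained over adjusting for that rate. All of this stands, and it limits the point to a precision improvement and a missing sensitivity check.

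Four stronger readings are tempting, and the documents do not support them.

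- *The correct ICC was available in the extract.* At the plan's 10% prevalence, about 90% of the children in it would lie outside the primary population. An all-children ICC also reflects differences between practices in VHP share, so it may lie above or below the ICC among children of VHPs.
- *The power calculation ignored data in hand.* Under C.6.e, covariates are collected once practices have agreed to take part, so they could inform a re-check but not the proposal-stage calculation.
- *Model adjustment rests on the up-to-date rate.* C.6.j never says so. The gap is that no such covariate is named.
- *The baseline uses a different vaccine list.* C.6.e.4 refers to all recommended childhood vaccines without listing them. Only the difference in metric is clear.

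Finally, the text already contains COVID-19 procedures and a survey for summer 2020, so randomization may be complete. That would remove the balancing use but not the covariate use.

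**Conclusion.** The point holds as a worthwhile improvement in design and reporting. The baseline metric is coarser than the outcome it stands for, no practice-level baseline of the outcome is pre-specified for the model, and the ICC is the one clustering input left unvaried.

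The margin is narrow. The claim of at least 90% power survives an ICC up to about 0.026 to 0.033, and at 0.05 power is about 80-83%. The benefit of the better covariate depends on an unknown correlation and matters mainly if the ICC is well above 0.02.

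A reader might infer that the trial is underpowered. The documents do not show that on this ground: the stated design gives 92.6-94.6%, and the outcome's true ICC could be on either side of 0.02. That 0.02 is itself a hesitancy ICC is inferred from the shared citation and that trial's primary outcome.

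The gap between the planning SD of 20 and the preliminary SD of 29.8 is a separate matter with a larger effect on power (66.7% at 300 per arm, normal).

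**What to change.** 1. **C.6.e.4:** keep the up-to-date rate, and also score the extract with the C.6.i formula, cut at 19 months 0 days, for all children aged 19-35 months. This assumes that the extract carries dose dates.
2. **C.6.j:** pre-specify the practice mean percentage of days under-immunized as a covariate in model (1), regardless of observed imbalance and alongside the variables used to constrain randomization.
3. **C.6.e:** use the rescored mean in the balance criterion only if randomization is still open.
4. **C.6.k:** add power over an ICC range such as 0.02-0.05. Report the all-children ICC as a proxy check on 0.02, labelled as not being the ICC among children of VHPs.

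If the check pointed to 0.05, 90% power without the covariate would need about 532 per arm (normal, 12 practices per arm). That is 2 × 532/0.10 = 10,640 parents approached, within the 12,000 that C.6.k already calls feasible.

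**Cost:** modest programming on data already being requested, a sentence or two in each section, and one between-practice degree of freedom. The stated power may become less favourable.

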C.6. Aim 2: To evaluate the impact of the PIVOT with MI intervention on child immunization status at 19 months of age.

C.6.a. Overview and Design: We propose to conduct a cluster RCT (Figure 3). We will randomize PSPRN and COCONet practices (N=24) to control and intervention arms using a covariate-constrained randomization approach. All parents of newborn infants receiving health supervision at a study practice will be screened for vaccine hesitancy at their child's initial visit using the PACV-SF (see C.1.a.) in order to identify VHPs, the primary study population. Providers at intervention practices will receive the proposed 5-component PIVOT with MI provider training program (see C.5.b.). Providers at control clinics will give usual care. A subset of VHPs at intervention clinics who give us permission to contact them will have their child's health supervision visit videotaped to assess intervention fidelity. Our main outcome will be child immunization status at 19 months expressed as the mean percentage of days under-immunized from birth to 19 months.

[figure not shown]
C.6.b. Setting and Population: Two regional PBRNs (PSPRN and COCONet) from 2 states (Washington and Colorado) will serve as the study setting (see C.2.). Both Washington and Colorado are ideal settings to conduct a study of an intervention designed to improve immunization rates among VHPs because both have a high prevalence of VHPs, with each ranking in the highest quintile among US states with respect to the proportion of parents claiming non-medical exemptions for their child from required school-entry vaccines.²

C.6.c. Eligibility: Providers will be eligible if they belong to PSPRN or COCONet. All English- and Spanish-speaking parents with a newborn infant <1 month old receiving health supervision at a participating practice during the intervention period will be eligible. VHPs, defined as those who have a positive PACV-SF (see C.1.a.), will constitute our primary study population because we are most interested in changing their vaccination behavior.^{10,27} VHPs at intervention practices who indicate on the PACV-SF that study staff can contact them about participation in additional study activities will be eligible for the fidelity study (Aim 2a).

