C.6.j. Analysis: We will conduct an intention-to-treat analysis. The patient will be the unit of analysis. We will examine baseline characteristics of parents in control and intervention arms using Pearson's χ^2 tests (or Fisher's exact tests) for categorical variables and t-tests for continuous variables to assess for any unbalanced confounders. Any unbalanced confounders will be controlled for as covariates in all subsequent regression analyses. We will also compare baseline characteristics between parents with and without missing data. We will apply sensitivity analysis and multiple imputations techniques to address missing data.

Given the nested structure of the data, we will apply mixed effects regression models to examine the effects of the intervention on our primary outcome while controlling for covariates and accounting for correlations due to clustering. Let y_{ijk} denote the percent days under-immunized for child k who receives care from provider j at clinic i , let T_{ijk} be the intervention indicator (0=control, 1=intervention) for the child, let X_{ijk} be the collection of covariates that includes potential confounders (at patient, provider, or practice levels), then a mixed model that accounts for this specific nesting data structure can be specified by

$$y_{ijk} = T_{ijk}\alpha + X_{ijk}\beta + Z_{ijk}^{(3)} u_i^{(3)} + Z_{ijk}^{(2)} u_{ij}^{(2)} + \epsilon_{ijk}, \quad (1)$$

for $k = 1, \dots, n_{ij}$ first-level observations (patient) nested within $j = 1, \dots, M_i$ second level groups (provider), which are nested within $i = 1, \dots, M$ third-level groups (practices). $Z_{ijk}^{(3)}$ and $Z_{ijk}^{(2)}$ are design matrices for the third- and second-level random effects. Further normality and independence assumptions will be placed on random effects and error terms if the outcome is continuous. The above model specification represents a multi-level linear mixed model. Parameter estimates will be obtained through restricted maximum likelihood estimation. Robust sandwich standard error estimates to account for the clustering will be used for inference. In the above model specification, the parameter α captures the expected difference between intervention and control arms and will be our focus of inference. For binary outcomes, the above model specification can be adapted to mixed effects logistic regression with similar estimation and inference techniques.¹¹⁸

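### Hepatitis B birth-dose status at enrolment is a baseline vaccination measure, but the primary analysis would adjust for it only if a baseline test flagged imbalance

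*Combined protocol and SAP*

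**What the plan says.** Section C.6.i gives the outcome for children of vaccine-hesitant parents (VHPs) as immunization status "expressed as the mean percentage of days under-immunized from birth to 19 months for 22 doses of 8 vaccines". Three of the 22 doses are hepatitis B. On the calculation it states "we will sum the days late for each dose and divide this by the maximum number of days a child could be late" on all doses. No rule starts the count at enrolment.

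Entry comes after birth. Under C.6.c, "parents with a newborn infant <1 month old receiving health supervision at a participating practice during the intervention period will be eligible", and under C.6.a parents "will be screened for vaccine hesitancy at their child's initial visit using the PACV-SF". The footnote to Table 1 explains how the PACV-SF item on past delay applies at this age: "Only delay of the birth dose of the hepatitis B vaccine would be relevant for parents of children ≤ 2 months old". The protocol therefore treats delay of the birth dose as something that can already have happened at screening.

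Section C.6.j compares baseline parent characteristics between arms by chi-squared, Fisher or t-tests and then states: "Any unbalanced confounders will be controlled for as covariates in all subsequent regression analyses". Model (1) has a general covariate term that allows patient-, provider- and practice-level confounders but names no variable. The items that C.6.g adds to the PACV-SF are demographic. The four balancing variables in C.6.e are practice-level.

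**The concern.** Birth-dose status is the one piece of the child's own vaccination history that can exist at entry. It is a component of the outcome and, through PACV-SF item 1, it also helps decide who counts as a VHP. A parent who has already delayed one dose may well be more likely to delay later ones, which would make it a natural prognostic covariate.

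Under C.6.j, whether it enters the model depends on a baseline test. An imbalance that falls short of significance is left out even if the variable is strongly prognostic, and the final model is not known until the data are seen. With 12 practices per arm (if the 24 split evenly), chance differences between arms in prior vaccine behaviour are plausible. At stake are some power and some protection of the estimate against such a difference.

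**Working it through.** **Inputs.** From C.6.k: preliminary mean 26.2% and SD 29.8 (six vaccines); 37 days late per dose; target decrease 10 days; 600 pairs, 300 per arm, 25 at each of 24 practices; alpha 0.05 (taken as two-sided); planning SD 20, with SD 25 as the plan's own variation; ICC 0.02. The units of the SD are not stated and are read here as percentage points.

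**1. The plan's power.**
- Effect: 10/37 × 26.2 = 7.08 points.
- Design effect: 1 + 24 × 0.02 = 1.48.
- SE = SD × √(2 × 1.48/300). At SD 20 this is 1.987, so effect/SE = 3.56 and power is 94.6% by the normal approximation, or 92.6% with a t distribution on 22 df.
- The stated 90% or more is reproduced. Reading both 10 and 20 as days gives 99.9%.

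**2. Direct contribution of late days before enrolment.**
- 37 days corresponds to 26.2%, so the implied maximum is 37/0.262 = 141 late days per dose, or about 3,107 over 22 doses. Carrying the six-vaccine figure over to eight vaccines is an assumption.
- A birth dose counted late from day 0 to an entry visit on day 3, 7, 14 or 30 adds 100 × days/3,107 = 0.10, 0.23, 0.45 or 0.97 points for that child.
- With assumed denominators of 6,600 to 9,900 days, 30 days adds 0.45 to 0.30 points.
- If an assumed 10-40% of VHP children missed the dose, a one-SE chance difference in prevalence is √(2 × p(1−p) × 1.48/300) = 3.0-4.9 percentage points. Multiplied by at most 0.97, this shifts the arm difference by about 0.03-0.05 points, which is negligible.

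**3. Contribution through later lateness.** This needs an assumed gap in outcome between children with and without the birth dose. The same one-SE imbalance shifts the arm difference by 0.6-1.0 points if the gap is 20 points and by 1.2-1.9 points if it is 40, against a target of 7.08. The documents give neither gap.

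**4. Power with the covariate fixed.** Let it explain a share R² of child-level variance, with clinic variance unchanged at 0.02 of the total. Then SE = SD × √(2 × [0.02 × 25 + 0.98 × (1 − R²)]/300). The bracket is 1.48 at R² = 0, 1.431 at 0.05 and 1.235 at 0.25.

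| SD | Unadjusted | R² = 0.05 | R² = 0.25 |
|---|---|---|---|
| 20 (planning) | 94.6% | 95.2% | 97.4% |
| 25 (plan's variation) | 81.4% | 82.6% | 87.7% |
| 29.8 (preliminary) | 66.7% | 68.2% | 74.5% |

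All cells use 600 pairs and the normal approximation. At SD 25 the plan itself would approach 12,000 parents, so that row shows the covariate's effect at fixed size and does not contradict the plan's claim.

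**The case against.** The randomized comparison is valid without this covariate, and at the planning SD power already exceeds 90%. No R² is given, so every gain is hypothetical, and the larger ones use SDs above the planning value, which is a separate sample-size question. This stands and limits the weight of the point.

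Lateness before enrolment is not itself established. The documents do not say on what day the birth dose becomes late. C.6.k refers to a 30-day window for most doses; if that applied, late days before entry would be close to zero. Late days on this dose after entry remain open to the intervention and belong in the outcome. This also stands, and is why the argument rests on prediction of later lateness rather than on the clock starting at birth.

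The variable is not absent from the plan. PACV-SF item 1 records delay of the birth dose by parent report, and model (1) could take it in if a test flagged it. Constrained randomization balances practice percent VHP, measured partly by that item, and practice immunization rates, separately by state. Both help. However, the first route is conditional on a test, and the second does not balance birth-dose status among the VHPs enrolled later.

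A reader might infer that counting from birth biases the treatment effect. The documents do not support that: practices are randomized, and the direct contribution is tiny. A reader might also apply R² to the whole variance, including the clinic part, and obtain 78.9% power at SD 29.8 with R² = 0.25. A variable assumed to explain child-level variance does not remove clinic variance, and the figure is then 74.5%.

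**Conclusion.** The point holds as one of precision and chance imbalance. A baseline vaccination variable tied to both the outcome and the entry screen is left to a significance test when it could be a planned covariate.

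The benefit is modest. Over the assumed R² range of 5-25% the power gain is about 0.6 to 2.8 percentage points at SD 20 and about 1.5 to 7.8 at SD 29.8. In no row does it lift a design below 90% to 90%. These figures rest on the assumed R², an unchanged clinic variance, percentage-point units for the SD, and a 7.08-point effect derived from the plan's 10 days. If birth-dose status hardly predicts later lateness, the gain is close to nil. The change is still worth making, because it removes a data-dependent choice about this variable at almost no cost.

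**What to change.** In C.6.j, take this variable out of the test-then-adjust rule and state that the primary model includes, regardless of observed balance, a fixed child-level covariate: hepatitis B birth dose recorded in the state registry with a date before the PACV-SF visit (yes/no). Doses given at that visit or later do not count as baseline. Keep the outcome definition as it is. Recomputing the percentage without hepatitis B dose 1 can be an optional sensitivity analysis.

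The cost is one sentence, one variable derived from registry data already being obtained for the outcome, and one child-level degree of freedom among about 600 pairs. One caveat should be written down: the covariate is assumed to be unaffected by the intervention. That may not hold for families with an older child already seen at an intervention practice, since recruitment runs for 18 months after the baseline training.
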